2.4. IMGC936 Benefit/Risk in Humans

IMGC936 is an investigational drug with safety data available from nonclinical studies. No information is available about the adverse effects of IMGC936 in humans; therefore, as with any new product, administration of IMGC936 may involve risks that are currently unforeseen.

IMGC936 is an ADC that may lead to killing of the tumor cell. Based on the mechanism of action and the risks associated with similar drugs, infusion-related reactions, hematologic toxicity, ocular toxicity, and interstitial cystitis are potential risks of IMGC936 treatment.

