4.2.1. Hematologic Dose-Limiting Toxicity

Hematologic DLT is defined as follows:

- Grade 4 neutropenia lasting > 7 days
- \geq Grade 3 febrile neutropenia Grade 4 thrombocytopenia, irrespective of duration
- Grade 3 thrombocytopenia associated with clinically significant bleeding
 - \geq Grade 3 hemolysis

The following events will be specifically **excluded** from the definition of hematologic DLT:

- ≥ Grade 3 lymphopenia
- Grade 3 anemia that is not associated with other clinically significant complications

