7.7.1. Neutropenia

- Grade 1 or Grade 2 No specific therapy required.
- Grade 3
 - Hold study drug until recovery to \leq Grade 1.
 - Monitor neutrophil counts weekly until recovery to \leq Grade 1.
 - Discontinue study drug if not recovered to ≤ Grade 1, within 21 days.
 - Restart study drug at the same dose level if recovered to ≤ Grade 1 within 21 days.
 - Consider secondary prophylaxis with granulocyte colony-stimulating factor (G-CSF) for subsequent cycles.
- Grade 4
 - Hold study drug until recovery to \leq Grade 1.

- Monitor neutrophil counts weekly until recovery to \leq Grade 1.
- Discontinue study drug if not recovered to ≤ Grade 1 within 21 days.
- Restart study drug with one level dose reduction if recovered to \leq Grade 1.
- Consider secondary prophylaxis with G-CSF for subsequent cycles.

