## 7.2. Adverse Events (AEs)

AEs will be documented on the AE eCRF and monitored continuously throughout the study from the time of informed consent until 30 days after the patient's last study drug or until the event has resolved, stabilized, or returned to baseline. AEs attributed to study procedures, including those events that occur prior to the first dose, should also be documented on the AE eCRF.

AE data are available to ImmunoGen from 2 sources, the eCRFs and the serious adverse event (SAE) forms. While reconciliation will be performed, the production of data summaries and listings will be based on the data collected on the eCRF.

Pre-treatment AEs are defined as AEs with an onset date prior to the first dose of study drug. TEAEs are defined as AEs with an onset date on or after the first dose of study drug, and within 30 days of the last dose of study drug or prior to the start of a new anti-cancer treatment, whichever occurs first. Medical history conditions that exist before the initiation of study drug but worsen in severity during the study will also be recorded on the AE eCRF as an AE and will be included as treatment-emergent in the summary tables and listings.

The adverse events will be coded using MedDRA, associating lower-level terms with PT and SOC by the primary hierarchy. The tables will display the counts and percentages of patients who reported at least 1 TEAE in each SOC represented in the AE data. Within each SOC, the tables will display the counts and percentages of patients reporting at least 1 TEAE as designated by the PT.

AEs are graded using Common Terminology Criteria for Adverse Events (CTCAE) Version 5.0. AE summaries may include summaries for all AEs and by the maximum CTCAE grade for the item being summarized (ie, SOC or PT). In these cases, the outputs will include a row for All Grades as well as rows for the 5 potential CTCAE grades, Grade 1 (Mild), Grade 2 (Moderate), Grade 3 (Severe), Grade 4 (Life threatening or disabling), or Grade 5 (Death). AEs missing a severity grade will not be included in the Grade 1-5 rows of the tables. An AE reported by a patient more than once will be represented in the most severe category.

Ocular AEs including blurred vision events and grouped keratopathy events will be analyzed for outcome, resolution, time to onset and time to resolution. Patients at 6mg/kg who administered different prophylactic eye drops will be further analyzed.

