- TEAEs leading to death

The following PTs will be grouped for the analyses:

AEPT3	PTs		
Keratopathy	"Corneal cyst", "Corneal disorder", "Corneal epithelial microcysts",		
	"Keratitis", "Keratopathy", "Corneal opacity", "Corneal erosion",		
	"Corneal pigmentation", "Corneal deposits", "Keratitis interstitial",		
	"Punctate keratitis", "Corneal epithelium defect", "Corneal epithelial		
	microcysts", "Limbal stem cell deficiency"		
Blurred vision event	"Vision blurred", "Visual impairment", "Vitreous floaters", "Visual		
	acuity reduced", "Diplopia", "Presbyopia", "Accommodation disorder",		
	"Refraction disorder", "Hypermetropia"		
Dry eye	"Lacrimation decreased", "Dry eye"		

AEPT3	PTs
Cataract	"Cataract", "Cataract nuclear", "Cataract cortical"
Eye pain	"Eye pain"
Ocular discomfort "Eye pruritus", "Eye irritation", "Ocular discomfort", "Foresensation in eyes"	
Peripheral neuropathy "Neuropathy peripheral", "Peripheral sensory neuropathy", "Peripheral sensory neuropathy", "Peripheral sensorimotor neuropathy", "Peripheral sensorimotor neuropathy"	
Pneumonitis "Pneumonitis", "Interstitial lung disease", "Pulmonary fibrosis", "Organizing pneumonia", "Organising pneumonia"	
Abdominal pain "Abdominal pain", "Abdominal pain upper", "Abdominal pain lo "Abdominal discomfort"	
Fatigue	"Fatigue", "Asthenia"
Dyspnea	"Dyspnea", "Exertional dyspnea"
Hypertension	"Hypertension", "Increased blood pressure", "High blood pressure"
Hypokalaemia	"Hypokalaemia", "Blood potassium decreased"
Hyponatraemia	"Hyponatraemia", "Blood sodium decreased"
Hypomagnesaemia	"Hypomagnesaemia", "Blood magnesium decreased"
Thrombocytopenia	"Thrombocytopenia", "Platelet count decreased"

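### The SAP's grouped-term list merges clinical and laboratory terms for platelets and electrolytes but not for neutrophils, so PT-level adverse event tables may not show a combined neutropenia incidence

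*SAP*

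**What the plan says.** SAP 7.2 introduces its grouping table with "The following PTs will be grouped for the analyses". Sixteen groups follow, with no wording that leaves the list open. Most collect ocular or other clinical synonyms. Four pair a clinical term with a laboratory one: thrombocytopenia with decreased platelet count, and the low-potassium, low-sodium and low-magnesium terms with the matching decreased blood level. No group covers neutrophils, hemoglobin or white cells.

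The same section sets the counting rule: "Within each SOC, the tables will display the counts and percentages of patients reporting at least 1 TEAE as designated by the PT".

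Protocol 2.4 says that "infusion-related reactions, hematologic toxicity, ocular toxicity, and interstitial cystitis are potential risks of IMGC936 treatment". Protocol 4.2.1 lists "Grade 4 neutropenia lasting > 7 days" among the hematologic dose-limiting toxicities, next to thrombocytopenia. Protocol 7.7 has two parallel subsections, 7.7.1 for neutropenia and 7.7.2 for thrombocytopenia. Section 7.7.1 calls for holding study drug at Grade 3 and Grade 4 and includes "Discontinue study drug if not recovered to ≤ Grade 1, within 21 days".

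**The concern.** The list treats two closely parallel toxicities differently and gives no reason. A participant with low platelets is counted once in a thrombocytopenia row, whichever term the site used. A participant with low neutrophils may be counted in either of two rows, or in both.

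Mixed recording is foreseeable from the protocol. Under Clinical Laboratory Changes in section 12.2.1, a laboratory abnormality is reported as an adverse event when it leads to an intervention. Where there are clinical sequelae, the diagnosis is reported instead of the laboratory finding. One toxicity can therefore enter the database under either kind of term.

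What is at stake is how tolerability is described. It is a primary objective in escalation and a secondary one in expansion, and the SAP summarizes safety by dose level. If neutropenia is split, its rows cannot be compared with the thrombocytopenia row. A reader also cannot add the two rows safely, because a participant may appear in both.

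**Working it through.** The documents give no neutropenia incidence and no coding split, so there is no planned figure to reproduce. The check has three parts.

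**1. Which tables are exposed.** SAP 7.2 lists 17 adverse event summary tables. Five cannot be affected: the overall summary (participants with any event of a type), the table of all deaths, and the three ocular tables. That leaves 17 − 5 = 12 that could carry preferred-term rows: all events; Grade 3 or higher; related; related Grade 3 or higher; serious; non-serious; related serious; leading to discontinuation; leading to interruption; related leading to discontinuation; related leading to interruption; and leading to death.

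**2. What two rows can tell the reader.** Let *a* participants have the clinical term, *b* the laboratory term, and *n* be the group size. The combined incidence lies between max(*a*, *b*)/*n* and min(*n*, *a* + *b*)/*n*. The two rows alone do not say where in that range it falls.

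**3. Illustration under stated assumptions.** Each affected participant is coded to one term only. The affected counts are assumed. Of the group sizes, 39 is a full expansion cohort and 15 is the largest expanded escalation cohort.

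| Affected / n | Combined | Split of participants | Larger single row |
|---|---|---|---|
| 8 / 39 | 20.5% | 8 and 0 | 20.5% |
| 8 / 39 | 20.5% | 7 and 1 | 17.9% |
| 8 / 39 | 20.5% | 6 and 2 | 15.4% |
| 8 / 39 | 20.5% | 4 and 4 | 10.3% |
| 6 / 15 | 40.0% | 6 and 0 | 40.0% |
| 6 / 15 | 40.0% | 5 and 1 | 33.3% |
| 6 / 15 | 40.0% | 4 and 2 | 26.7% |
| 6 / 15 | 40.0% | 3 and 3 | 20.0% |

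Two rows of 4 in 39 are compatible with any combined incidence from 4/39 = 10.3% to 8/39 = 20.5%. In an escalation cohort of 6 with 2 affected, one under each term, each row shows 1/6 = 16.7% where the combined figure is 2/6 = 33.3%. A grouped row would show the combined figure in every case. The shortfall is zero when coding is uniform, and also when every participant with one term has the other.

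**The case against.** Several points on the other side stand.

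- **A reader might infer that neutropenia is understated, and in every adverse event table.** The documents do not support that. Five of the 17 tables are unaffected. In the other 12, each row is correct for its own term and no participant is lost. Only a combined figure may be missing, and only if coding is mixed, which nothing in the documents establishes.
- **Neutrophil grades are reported elsewhere.** SAP 7.3 derives CTCAE grades from laboratory values and gives shift tables from baseline to worst value, with hematology in scope. These do not depend on event coding, and they arguably measure cytopenia better than event reports, which depend on an intervention or investigator discretion. But SAP 7.3 says its grades leave out clinical evaluations, so they carry no relatedness, seriousness or action taken. Listings of related, serious, interruption and discontinuation events are planned. In small cohorts a reader could count from them by hand, but a hand count does not replace a summary row.
- **No decision rule depends on the grouping.** Dose-limiting toxicities, escalation and the expansion pause (Protocol 4.2 to 4.4) do not use preferred-term rows. This limits the importance of the point.
- **The protocol asks only for system organ class and preferred term displays** (section 14.5.1), and the SAP provides them. The inconsistency lies within the SAP's own list.
- **Anemia is a weaker case.** The named risk is hematologic toxicity as a class. Protocol 4.2.1 excludes "Grade 3 anemia that is not associated with other clinically significant complications" from dose-limiting toxicity, and section 7.7 has no anemia rule.
- **The separate laboratory term for neutrophils is inferred** from the platelet and electrolyte rows. The documents do not show it.

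A reader might also suspect from their spelling or form that the dyspnea and hypertension entries do not match coded terms. That depends on a dictionary outside the documents, and the list itself mixes American and British spellings, so no conclusion follows.

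**Conclusion.** The gap is real but minor. The list departs from its own principle by leaving neutrophils out, and the protocol gives no reason to treat neutropenia differently from thrombocytopenia. If both kinds of term are used, at most 12 of the 17 summary tables will split neutropenia. No row will then show the combined incidence by relatedness, seriousness, Grade 3 or higher, or action taken.

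The size is unknown. It ranges from nothing under uniform coding to half the combined rate in each row under an even, non-overlapping split. The incidences used to show this are assumptions, not trial data. The conclusion also assumes that the coding dictionary holds a separate laboratory term for low neutrophils, as the platelet row suggests. This is a worthwhile improvement to reporting. It is not evidence that the planned tables are biased.

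**What to change.** Add a neutropenia group to the SAP 7.2 list, combining the clinical term with the laboratory term for decreased neutrophil count and keeping febrile neutropenia separate. With lower priority and on the same principle, add an anaemia group combining the clinical term with the laboratory term for decreased hemoglobin. Check the exact term names against the MedDRA version in use. Keep the ungrouped preferred terms in the listings so that no detail is lost. If the omission was deliberate, a sentence giving the reason would do instead.

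The cost is a few lines in one SAP table and in the programming look-up for grouped terms. No data collection, sample size or decision rule changes. Settling the grouping before results are reviewed avoids a post hoc choice.

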# 7.3. Clinical Laboratory Results

Laboratory test results (including hematology, coagulation, serum chemistry, and urinalysis) and abnormal laboratory values will be presented in data listings.

CTCAE Version 5.0 laboratory grades will also be presented. CTCAE grades will be derived based on laboratory results and will not factor in clinical evaluations.

Shift tables summarizing the changes from baseline to worst post-baseline values (high or low, as applicable) in severity of laboratory grades will be summarized by CTCAE grade.

Clinically significant values in liver function tests (LFTs) will be summarized by the following categories, using the maximum lab value among visits. The denominator for the summaries will be the number of patients who had at least 1 non-missing post-baseline value within 30 days of the last dose of study drug or prior to the start of a new anti-cancer treatment, whichever occurs first. The categories for each test are not mutually exclusive:

- Aspartate aminotransferase (AST)
  - $> 3 \times ULN$
  - $> 5 \times ULN$
  - $> 10 \times ULN$
  - $> 20 \times ULN$
- Alanine Aminotransferase (ALT)

- $> 3 \times ULN$
- $> 5 \times ULN$
- $> 10 \times ULN$
- $> 20 \times ULN$
- AST or ALT
  - $> 3 \times ULN$
  - $> 5 \times ULN$
  - $> 10 \times ULN$
  - $> 20 \times ULN$
- Total bilirubin (TBL)
  - > ULN
  - $> 2 \times ULN$
- Alkaline phosphatase (ALP)
  - > 1.5 × ULN
- (AST or ALT) and TBL (concurrent)
  - AST or ALT  $> 3 \times ULN$  and TBL  $> 1.5 \times ULN$
  - AST or ALT  $> 3 \times ULN$  and TBL  $> 2 \times ULN$
- (AST or ALT) and ALP and TBL (concurrent)
  - AST or ALT  $> 3 \times$  ULN and ALP  $< 2 \times$  ULN and TBL  $> 2 \times$  ULN

Here, concurrent means that all the associated LFTs must be from the same visit.

Results from pregnancy tests will be provided in listings.

# 7.4. Vital Signs

Vital signs (including temperature, pulse rate, systolic blood pressure (BP), diastolic blood pressure, and respiratory rate) will be collected throughout the study.

Vital signs results will be classified into 4 or 5 categories (low, borderline low, normal, borderline high, or high) according to Table 3 below. Shift tables based on this classification will be summarized from baseline to the last post-baseline visit value.

**Table 3:** Classification of Vital Signs

Vital Sign	Low	Borderline Low	Normal	Borderline High	High
Heart Rate (beats per minute)	< 50	50-59	60-90	91-99	≥ 100
Systolic BP (mmHg)	< 80	-	80-120	121-139	≥ 140

Vital Sign	Low	Borderline Low	Normal	Borderline High	High
Diastolic BP (mmHg)	< 60	-	60-80	81-89	≥ 90
Respiratory Rate (breaths per minute)	< 12	-	12-20	21-24	≥ 25
Temperature (°C)	< 35.0	35.0-36.4	36.5-37.2	37.3-37.9	≥ 38.0

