12.2.3. Protocol-Specific Adverse Events of Special Interest

IMGC936 has 1 AESI: IRR. Any symptom or sign occurring within 24 hours of infusion and suggestive of an IRR should be promptly reported as per Section 12.2.5.

Further information on risks can be found in the IMGC936 Investigator's Brochure.

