14.5.3. Other Safety Endpoints

Twelve lead ECGs will be collected and analyzed for evidence of cardiac toxicity, especially prolongation of QT interval. Change in LVEF from baseline will be summarized. Vital signs will be summarized with descriptive statistics at each visit and time point at which they are collected. Shift tables may be created.

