toxicity is observed during escalation, ocular symptom assessment will occur on Day 1 of each cycle or more frequently if ocular symptoms and signs are observed. Phone-based ocular symptom assessments are acceptable if no clinic visit is scheduled.

- ^h Females of childbearing potential only. Serum pregnancy test is required for eligibility. Subsequent pregnancy tests may use serum or urine. Results must be reviewed before study drug infusion on Day 1 of Cycle 1 and all subsequent cycles. If screening test is performed within 72 hours of first infusion, repeat of the test on Day 1 may be deferred.
- During non-dosing visits (eg, screening and EOTV), vital signs will be taken at one timepoint. For Cycle 1 Day 1, vitals are measured pre-infusion (within 30 minutes before); 15 and 30 minutes after start of infusion (± 5 minutes); EOI (± 10 minutes); and 2, 4, and 6 hours after EOI (± 10 minutes). For Cycle 2 Day 1 and subsequent cycles, vitals are measured pre-infusion (within 30 minutes before), EOI (± 10 minutes), and 1 hour after EOI (± 10 minutes). Participants in dose escalation cohorts must have vital signs recorded on both dosing and non-dosing days through treatment Cycle 3. Beginning on Cycle 4, vital signs must be recorded on Day 1 of each treatment cycle. Participants in expansion cohorts must have vital signs recorded on Day 1 of each treatment cycle.
- ^j To be obtained pre-infusion. Day 1 laboratory samples can be obtained up to 3 days before infusion. Chemistry and hematology results must be reviewed before study drug administration. See Appendix 3 for assessments. Beginning on Cycle 4, laboratory samples only required on Day 1 of each cycle.
- ^k Tumor markers are obtained as indicated for each specific tumor type, eg, CEA for colorectal cancer and CA19-9 for pancreatic cancer. Repeat collection on Cycle 1 Day 1 if screening collection > 7 days prior.
- Tumor assessments are Q6W (\pm 7 days) while participant is on study drug, then Q12W (\pm 21 days). Assessments continue until discontinuation criteria are met. Tumor assessments are performed at EOTV except if prior assessment was \leq 30 days of EOTV and results are available for RECIST v1.1 assessment.
- ^m Tumor assessments will occur after participant has discontinued study drug Q12W (± 21 days) until evidence of PD, initiation of another anticancer therapy, withdrawal of consent, LTFU, death, or end of study, whichever occurs first.

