#### 1. INTRODUCTION

## 1.1. Background

This document describes the statistical analysis plan (SAP) for the study IMGC936-0901, based on the Protocol Amendment #3, dated on 29-March-2022.

This SAP will govern the analysis of this study. Any deviations from the SAP will be documented as such in the study report.

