# 4.4. Multiple Assessments for the Same Assessment Time Point

In general, no by-visit analyses is planned for this study, unless otherwise indicated for a specific parameter.

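### SAP 7.4 tabulates vital signs only as a shift to the last post-baseline visit and drops, without explanation, the visit and time-point summary promised in Protocol 14.5.3

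*SAP*

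**What the plan says.** Protocol 14.5.3 makes a firm commitment: "Vital signs will be summarized with descriptive statistics at each visit and time point at which they are collected". It then adds an option: "Shift tables may be created".

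SAP 7.4 sorts each vital sign into four or five bands from low to high and specifies one table: "Shift tables based on this classification will be summarized from baseline to the last post-baseline visit value". It does not mention descriptive statistics, visits or infusion-day time points.

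The general rule in SAP 4.4 is: "In general, no by-visit analyses is planned for this study, unless otherwise indicated for a specific parameter". SAP 7.4 indicates no exception for vital signs. SAP 4.12 produces summary tables only where Sections 5 to 7 specify them. On precedence, SAP 1.1 says: "This SAP will govern the analysis of this study".

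The readings are concentrated around infusions. Under the vital-sign footnotes of Appendices 1 and 2, Cycle 1 Day 1 has one reading before the infusion and six after it starts: at 15 and 30 minutes, at end of infusion, and 2, 4 and 6 hours later. Later dosing days have three readings: before infusion, at end of infusion and one hour after (for Schedule B this is stated up to Cycle 3). A non-dosing visit such as the EOTV has one.

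Protocol 12.2.3 names a single event of special interest: "IMGC936 has 1 AESI: IRR".

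**The concern.** This is a first-in-human study of an intravenous drug, and its only event of special interest is a reaction to the infusion. The repeated readings on infusion days can show transient changes in blood pressure, heart rate or temperature, and how these vary with dose. A table that keeps only the last visit value mostly describes participants after dosing has stopped.

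The treatment of vital signs is also out of line with the rest of the SAP. For laboratory grades, SAP 7.3 specifies "Shift tables summarizing the changes from baseline to worst post-baseline values", high or low as applicable. SAP 7.5 gives QTcF categories by visit. SAP 7.11 tabulates visual acuity against the worst post-baseline result. No reason is given for using only the last value for vital signs.

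At stake is the dose-level picture of vital-sign changes that investigators did not report as adverse events.

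**Working it through.** The plan gives no figure to reproduce. The check has two steps: a comparison of the texts, and a count of the readings that can reach the table.

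**Step 1: does any other section restore the protocol's summary?**

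- Protocol 14.5.3 requires descriptive statistics at each visit and time point, with shift tables optional.
- SAP 7.4 has the shift table only.
- SAP 4.4 plans no by-visit analysis unless one is indicated for a parameter, and none is indicated here.
- SAP 4.12 produces no summary table beyond those named in Sections 5 to 7.

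The optional item has therefore become the only one, and the required item has gone. SAP 4.12 does promise listings of recorded data, although SAP 7.4 names none for vital signs.

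**Step 2: how many scheduled readings enter the table?**

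Assumptions: the participant completes one to three cycles, has every scheduled reading and attends the EOTV, which is the last visit analysed. Counts are per parameter.

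- Schedule A escalation. Cycle 1: 6 readings on Day 1 after the infusion starts, plus Days 3, 8 and 15, gives 9. Cycles 2 and 3: 3 on Day 1, plus Days 8 and 15, gives 5 each. EOTV: 1.
- Schedule A expansion (Day 1 of each cycle only). Cycle 1: 6. Each later cycle: 3. EOTV: 1.
- Schedule B escalation. Cycle 1: 6 on Day 1, 1 on Day 3, 3 on Day 8, 3 on Day 15 and 1 on Day 22, gives 14. Cycle 2: 3 + 1 + 3 + 3 + 1 = 11. Cycle 3: 3 + 3 + 1 = 7. EOTV: 1.

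Share entering the table = 1 / (scheduled post-baseline readings).

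| Setting | Cycles | Post-baseline readings | During or after an infusion | Share in the table |
|---|---|---|---|---|
| A, escalation | 1 | 9 + 1 = 10 | 6 | 10.0% |
| A, escalation | 2 | 10 + 5 = 15 | 6 + 2 = 8 | 6.7% |
| A, escalation | 3 | 15 + 5 = 20 | 8 + 2 = 10 | 5.0% |
| A, expansion | 1 | 6 + 1 = 7 | 6 | 14.3% |
| A, expansion | 2 | 7 + 3 = 10 | 8 | 10.0% |
| A, expansion | 3 | 10 + 3 = 13 | 10 | 7.7% |
| B, escalation | 1 | 14 + 1 = 15 | 6 + 2 + 2 = 10 | 6.7% |
| B, escalation | 2 | 15 + 11 = 26 | 10 + 6 = 16 | 3.8% |
| B, escalation | 3 | 26 + 7 = 33 | 16 + 4 = 20 | 3.0% |

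Under these assumptions, no reading in the fourth column reaches a vital-sign summary table. These are counts of scheduled readings. They do not estimate how many participants have an abnormal value, and the documents give no rate from which to do so.

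**The case against.** Four arguments can be made for the SAP as written.

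1. **Infusion reactions are captured elsewhere.** Any symptom or sign within 24 hours that suggests an infusion-related reaction must be reported. SAP 7.2 tabulates treatment-emergent events by preferred term, with further tables for Grade 3 or higher, related and serious events, interruption and discontinuation. SAP Section 7 presents safety summaries by dose level unless otherwise stated. This stands, and it narrows the point to excursions not reported as adverse events. One qualification: Protocol 14.5.1 lists a table of events of special interest, and the SAP 7.2 list does not include it. The reactions are still counted, but among all events.

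2. **The EOTV is not always last.** It is done where possible. A late EOTV, or one after new anticancer therapy, falls outside the SAP's safety window, and a participant still on drug at data cut-off has not had one. The last visit may then be a dosing day. This also stands, although SAP 7.4 does not say which of that day's readings is the visit value.

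3. **The protocol does not ask for a worst-value shift.** The SAP 7.4 bands are also not CTCAE grades, so the laboratory comparison is not exact. A worst-value proportion rises with the number of readings, and so with time on drug, which can distort comparisons between dose levels. This is a fair caution. It argues for showing the worst-value shift beside the last-value shift and reading it with exposure in view. It does not bear on the visit and time-point summary, which the protocol does require.

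4. **The SAP governs, and no decision rests on this table.** Dose-limiting toxicities are defined from adverse events and laboratory values. That limits the consequence. It does not explain the change: because the SAP governs, the promised summary will not be produced.

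**Conclusion.** The inconsistency between the documents is clear from the text. The governing SAP omits a summary that the protocol commits to, gives no reason, and keeps only a table that normally rests on one reading on a non-dosing day. Where the EOTV is the last visit, between 3.0% and 14.3% of scheduled post-baseline readings enter the table in the settings counted, and none of those comes from during or after an infusion. This assumes one to three completed cycles and full attendance.

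A reader might infer that infusion-related changes vanish from the report, or that infusion-period values can never be summarized. The documents support neither. Reported reactions and other adverse events are still tabulated by dose, general listings are promised, and a dosing-day value can enter the shift table when no EOTV is analysed.

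The effect is a moderate gap in safety reporting. Objective response rate, sample size and the escalation rules are untouched. The change is worth making because it is cheap and the readings are already scheduled.

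**What to change.** In SAP 7.4:

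- Restore descriptive statistics (value and change from baseline) by dose level at each visit and time point, including the infusion-day time points.
- Add a shift from baseline to the worst post-baseline value, high and low separately, and keep the last-value shift beside it. Note that worst-value proportions rise with the number of readings and time on drug, and should be read with exposure in view.
- State which reading is the visit value when the last visit is a dosing day, and name the vital-sign listing.
- State that baseline is the last value before the first infusion. SAP 4.2 goes by the date of first dose, which would admit readings taken after that infusion, whereas SAP Section 7 requires a value before the first dose.

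If the visit and time-point summary is left out on purpose, the SAP should give the reason for departing from Protocol 14.5.3. The cost is SAP wording and a few programmed tables, with no new data collection.
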